### 17.3 Analysis data sets

#### 17.3.1 *Full analysis set*

The Full Analysis Set (FAS) will consist of all subjects who have been randomized. This population will be used as the safety analysis set.

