#### 7.2.1 Secondary endpoints

The secondary endpoints are:

1. The difference in dental plaque acidogenicity, assessed by measuring pH in plaques, following tobacco-based snus substitution with either ZYN Dry or ZYN Moist for 4 weeks.
2. The difference in the counted number of cariogenic microorganisms in dental plaque following tobacco-based snus substitution with either ZYN Dry or ZYN for 4 weeks.
3. The difference in the amount of plaque, counted and scored 0-3, following tobacco-based snus substitution with either ZYN Dry or ZYN Moist for 4 weeks.
4. The difference in the degree of oral mucosal lesions, by presence, visual grading, and histopathological evaluation of biopsies, following tobacco-based snus substitution with either ZYN Dry or ZYN Moist for 4 weeks.
5. The difference in tooth discoloration, by means of colorimetry using a colorimeter and by visual shade grading using a shade guide, following tobacco-based snus substitution with either ZYN Dry or ZYN Moist for 4 weeks.

6. Frequency, intensity, and seriousness of AEs.

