#### 11.2.8 *Baseline symptoms*

A baseline symptom is defined as an event that occurs between the subject's signing of the ICF until the start of the randomization on the second treatment visit (*i.e.*, an event that occurs when the subjects are using their tobacco-based snus). Such events are not AEs and will be recorded as baseline symptoms in the Medical History Log in the eCRF.

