#### 11.6.1 *Definition of adverse event*

An adverse event (also known as adverse experience), abbreviated AE, is defined as any untoward medical occurrence in a subject administered a medicinal product (in this case an IP) and which does not necessarily have a causal relationship with this treatment. An AE can therefore be any unfavorable and unintended sign, symptom, or disease temporally associated with the use of a medicinal product, whether or not considered related to the IP.

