### 11.6.3 *Time period and frequency for collecting adverse events*

All AEs (including SAEs) will be collected by subject interview from the start of substitution of the subject's traditional tobacco-based snus with either ZYN Dry or ZYN Moist on Visit 3 (Day 0) until the last treatment visit (Visit 5, Day 28).

Any AE with start date on the day of the substitution of tobacco-based snus with ZYN must be recorded with start time.

At Visit 5, information on new AEs or SAEs, if any, and stop dates for ongoing events must be recorded as applicable.

Investigators are not obligated to actively seek AEs or SAEs after the conclusion of the study participation. However, if the Investigator learns of any SAE, including a death, at any time after a participant has been discharged from the study, and he/she considers the event to be reasonably related to the study intervention or study participation, the Investigator must promptly notify the Sponsor.

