### 17.6.6 *Analysis of adverse events*

An overview of all AEs, including SAEs, intensity, and deaths will be presented by SOC and PT. The incidences of AEs and SAEs will be summarized by SOC and PT by IP.

All AE data will be listed by subject and IP and will include the verbatim term entered by the Investigator.

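### The safety set is all randomized subjects, but an AE requires use of ZYN, so a randomized subject who never uses a pouch is counted as AE-free

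*Protocol*

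**What the plan says.** Protocol section 17.3.1 gives a single population for efficacy and safety. The full analysis set is everyone randomized, and the section adds: "This population will be used as the safety analysis set". It sets no condition on product use. Section 17.3.2 allows further datasets, but only for exploratory analyses.

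Adverse events are secondary endpoint 6 in section 7.2.1: "Frequency, intensity, and seriousness of AEs". Section 17.6.6 gives the summary: "The incidences of AEs and SAEs will be summarized by SOC and PT by IP". It names no denominator of its own, so the safety set of 17.3.1 applies.

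Section 11.6.1 defines an AE as an occurrence in a subject to whom an IP has been administered. Section 11.6.3 sets the collection period: AEs "will be collected by subject interview from the start of substitution of the subject's traditional tobacco-based snus with either ZYN Dry or ZYN Moist" at Visit 3, up to Visit 5. Events between consent and randomization are handled in section 11.2.8: "Such events are not AEs and will be recorded as baseline symptoms in the Medical History Log in the eCRF".

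Under section 8.1, randomization follows the Visit 3 assessments, the biopsy and the tooth cleaning. The subject then receives the products for ad libitum use. Section 17.4.3 reports the number of subjects treated with each product type but does not use that number to define a population.

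**The concern.** The population that can have an AE and the population that AEs are divided by are not the same. The protocol's definitions let only a user of ZYN have an AE, whereas its safety set admits anyone randomized. A subject who takes the products home, uses none and withdraws is tabulated as exposed and free of events. This can happen, because no supervised first pouch is described and section 10.5 says compliance is checked by asking the subject.

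At stake is the absolute AE incidence reported for each product type, which answers the safety and tolerability objective. Where the definition in 11.6.1 is applied, the error can only lower that incidence. The matter is also not left open for the statistical analysis plan: the protocol states the safety set outright, and its allowance for other datasets does not reach a secondary endpoint. A plan that used exposed subjects would depart from the protocol.

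**Working it through.** **Inputs from the protocol**
- Randomized: 46 in total, 23 per arm (sections 8.1, 9.3, 17.2).
- Fully evaluable target 40, dropout 15% (section 17.2).
- Safety set: all randomized (17.3.1).
- AE: needs administration of an IP (11.6.1); collected from the start of substitution (11.6.3).

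**Assumptions (the protocol gives neither)**
- k = randomized subjects in an arm who never use ZYN.
- x = subjects in that arm with at least one AE of the kind being tabulated.

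**Step 1: the plan's own figure.** 40 × 1.15 = 46, and 46 / 2 = 23 per arm. The stated number reproduces. (Dividing instead, 40 / 0.85 = 47.1, which is 48 in equal arms. That is a separate matter and does not affect this point.)

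**Step 2: the two incidences.**
- As planned: x / 23.
- Among users of ZYN: x / (23 − k).
- Ratio: (23 − k) / 23 = 1 − k/23, so the relative understatement is k/23 whatever x is.

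**Step 3: numbers.** For k = 0 the two agree. For k = 1 the understatement is 1/23 = 4.3% relative:

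| Subjects with the AE (x) | Users only, x/22 | All randomized, x/23 | Difference (points) |
|---|---|---|---|
| 1 | 4.5% | 4.3% | 0.2 |
| 3 | 13.6% | 13.0% | 0.6 |
| 5 | 22.7% | 21.7% | 1.0 |
| 10 | 45.5% | 43.5% | 2.0 |
| 15 | 68.2% | 65.2% | 3.0 |

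**Step 4: does replacement remove the effect?** No. Section 9.8.3 lets withdrawn subjects be replaced at the sponsor's discretion. A replaced never-user has still been randomized and stays in the safety set. The arm then has 24 randomized and 23 users, and the understatement is 1/24 = 4.2%.

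**The case against.** The best answer is that randomized and exposed should almost coincide here. Subjects have completed a four-week run-in on snus, randomization comes at the end of Visit 3, and the products are handed out at that visit to daily nicotine users who must give up all other nicotine products (section 9.6.1). This stands, and it is why 0 or 1 never-users per arm is the likely number.

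Second, section 17.4.3 presents the number treated, so a careful reader can see any gap and recompute the incidence. This also stands, but it does not make the planned table right.

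Third, the start of AE collection could be read as a calendar start on Day 0. Withdrawing subjects are asked about AEs (section 9.8.2), and the baseline-symptom window closes at randomization, so an event in a never-user might in practice be recorded as an AE. That ambiguity is real. The definition in 11.6.1 still excludes such an event, and counting it would put an event without exposure into a product's incidence, which is no better.

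Three stronger readings are tempting, and the protocol supports none of them:
- **The 15% dropout as a measure of never-use.** Applied to an arm of 23 it gives 0.15 × 23 = 3.45, so a reader might infer about three never-users. But the dropout rate covers everyone who falls short of four weeks of use and all visits. A subject who uses ZYN for ten days and leaves is a dropout and is exposed.
- **Confidence bounds on tolerability being distorted.** The protocol plans counts, percentages and listings for AEs, and no limits.
- **AEs charged to a product not used after a handout error.** Section 17.6.6 summarizes by IP, which can be read as product received, and section 10.4 keeps a log of what each subject was given. No such misattribution is shown.

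**Conclusion.** The point holds as a small, certain flaw in a stated rule. Under the protocol's own definitions, each randomized subject who never uses ZYN enters the denominator and cannot enter the numerator. In an arm of 23 this lowers AE incidence by 4.3% relative for one such subject, which is 0.2 to 3.0 percentage points for 1 to 15 subjects with events.

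The size rests on an assumed number of never-users. The effect is zero if every randomized subject uses ZYN, which may well be the outcome. The downward direction rests on 11.6.1 being applied as written.

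A reader might also infer a bias in favour of one product. Both arms receive the sponsor's products and there is no control arm, so nothing in the protocol favours Dry or Moist systematically. What falls is the absolute incidence in whichever arm has a never-user. This is a minor point, worth correcting because the correction is simple and standard.

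**What to change.** In section 17.3.1, replace the sentence on the safety set with one that defines it as all randomized subjects who used at least one ZYN pouch, summarized by the product type (Dry or Moist) actually used. That agrees with the summary by IP in 17.6.6 and settles how any handout error would be tabulated. Keep the full analysis set of all randomized subjects for the other endpoints.

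No new data collection is needed. The electronic pouch register (sections 8.1 and 10.5), the distribution log (10.4) and the return of unused product (10.6) can show whether a subject used ZYN. A short rule is needed for a subject whose register is empty but whose products were not all returned.

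The cost is one sentence in the protocol and a second population flag in the analysis data. The downside for the sponsor is that reported AE incidence may be slightly higher.

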#### 17.3.2 *Additional analysis datasets*

Additional datasets may be created as needed for exploratory analyses.

## 17.4 Description of study population

### 17.4.1 *Demographics and baseline characteristics*

Demographics, as well as the history of nicotine use, will be presented by descriptive statistics. All data will be listed by subject.

### 17.4.2 *Medical/surgical history and prior/concomitant medication*

Medical/surgical history will be presented by system organ classes (SOC) and preferred term (PT). Prior/concomitant medications will be presented by ATC level 1, 3 and 5 through descriptive statistics and listings.

### 17.4.3 *Treatment compliance*

The number of subjects treated with either ZYN Dry or ZYN Moist will be presented through descriptive statistics and listings.

### 17.4.4 *Oral examination*

Any abnormal findings at screening, *i.e.*, judged as outside the normal ranges by the Investigator, will be categorized as “abnormal, not clinically significant” or “abnormal, clinically significant” and presented in listings.

## 17.5 Analysis of the primary endpoint

### 17.5.1 *Difference in dental plaque acidogenicity between ZYN Dry and ZYN Moist*

The primary endpoint is the difference between ZYN Dry and ZYN Moist in terms of changes in dental plaque acidogenicity, assessed by measuring pH in plaques, after substitution of tobacco-based snus for 4 weeks. Assessment of dental plaque acidogenicity will be described using AUC6.2 to the observed dental plaque acidogenicity and presented using summary statistics as described in Section [17.1](#).

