## 7 STUDY OBJECTIVES AND ENDPOINTS

### 7.1 Primary objective

The primary objective of the study is to compare the impact on dental plaque acidogenicity after 4 weeks of substitution of tobacco-based snus with either ZYN Dry or ZYN Moist.

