#### 7.1.1 Primary endpoint

The difference between ZYN Dry and ZYN Moist in terms of changes in dental plaque acidogenicity, assessed by measuring pH in plaques, after substitution of tobacco-based snus for 4 weeks.

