## 17 STATISTICAL METHODS AND DETERMINATION OF SAMPLE SIZE

The principal features of the statistical analysis to be performed are described in this section. A more technical and detailed elaboration of the principal features will be presented in a separate Statistical Analysis Plan (SAP), which will be signed and approved prior to database lock.

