### 17.1 General

Continuous data will be presented in terms of evaluable and missing observations, arithmetic mean, standard deviation (SD), median, minimum and maximum value, Q1-Q3 (interquartile range [IQR]).

Categorical data will be presented as counts and percentages. When applicable, summary data will be presented by each group (ZYN Dry or ZYN Moist), and by assessment time. Individual subject data will be listed by subject number, treatment arm (ZYN Dry or ZYN Moist), and, where applicable, by assessment time.

All descriptive summaries and statistical analyses will be performed using SAS Version 9.4 or later (SAS Institute, Inc., Cary, NC).

Baseline will be defined as the last data collected before subjects are randomized into substitution of tobacco-based snus with either ZYN Dry or ZYN Moist.

No adjustment for multiple comparisons will be made.

No imputation of missing data will be performed.

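### The primary endpoint is a between-arm difference in change, but Section 17.5.1 specifies only descriptive statistics by arm and visit: no estimated difference, no confidence interval and no baseline adjustment

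*Protocol*

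**What the plan says.** Section 7.1 sets a comparative aim: "The primary objective of the study is to compare the impact on dental plaque acidogenicity after 4 weeks of substitution". Section 7.1.1 defines the endpoint as "The difference between ZYN Dry and ZYN Moist in terms of changes in dental plaque acidogenicity", and Section 17.5.1 repeats this definition.

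The analysis sentence in Section 17.5.1 reads: "Assessment of dental plaque acidogenicity will be described using AUC6.2 to the observed dental plaque acidogenicity and presented using summary statistics", and it refers the reader to the list in Section 17.1. For continuous data that list has counts of evaluable and missing values, then "arithmetic mean, standard deviation (SD), median, minimum and maximum value" and the quartiles, given by group and by assessment time, with individual listings. It also defines baseline as the last data before randomization, rules out imputation and says that multiple comparisons will not be adjusted for.

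The opening of Section 17 says that the principal features of the analysis are described there. A separate SAP is to elaborate them in more technical detail.

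Section 17.6.1, on the secondary acidogenicity endpoint, names the window Visit 3 to Visit 5. Section 17.5.1 names no window. Table 8.1-1 has plaque acidogenicity measured at Visits 2 to 5 (Days -28, 0, 14 and 28), and Section 9.9 places randomization at Visit 3 (Day 0).

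**The concern.** The endpoint is a contrast between arms, but the specified output is a set of one-arm summaries. Nothing in Sections 17.1 or 17.5.1 produces the difference itself or a measure of its uncertainty, and Section 17.5.1 does not say that change, rather than the AUC6.2 at each visit, is what will be tabulated. Section 17.1 mentions multiple comparisons, yet no comparison is specified anywhere in the protocol.

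At stake is how the main result can be read. With about 20 evaluable subjects per arm and no formal sample size calculation, sampling error is large. Two arm means without an interval do not show which differences the data exclude. No baseline adjustment is specified either, although the Day 0 value is collected on every randomized subject and would sharpen the comparison at no cost.

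**Working it through.** **Reading the sections together.**
- Estimand (7.1.1, 17.5.1): a difference between arms in change.
- Output (17.5.1 by way of 17.1): n, missing, mean, SD, median, minimum, maximum and quartiles by arm and visit.
- Not stated: a contrast, an interval, a test or a model.

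**Inputs from the protocol.** Section 17.2 aims for 40 evaluable and 46 randomized subjects at 15% dropout; Section 9.3 puts 23 in each arm. The 46 reproduces as 40 × 1.15 = 46. Dividing instead gives 40/0.85 = 47.06, and 46 × 0.85 = 39.1 expected evaluable. I use 20 per arm.

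**Assumptions.** The protocol gives no SD and no correlation between visits. I assume equal SD at each visit and a between-visit correlation ρ of 0.3, 0.5 or 0.7. Results are in single-visit SD units.

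**Base half-width.** t(0.975, 38) × √(2/20) = 0.640 for a variable with variance 1. For simplicity the same 38 degrees of freedom are used for every method. Each half-width is 0.640 × √(variance factor).

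| Method | Variance factor | ρ = 0.3 | ρ = 0.5 | ρ = 0.7 |
|---|---|---|---|---|
| Raw change from Day 0 | 2(1−ρ) | 1.40 → 0.76 SD | 1.00 → 0.64 SD | 0.60 → 0.50 SD |
| ANCOVA on Day 0 | 1−ρ² | 0.91 → 0.61 SD | 0.75 → 0.55 SD | 0.51 → 0.46 SD |
| ANCOVA on Day 0 and Day -28, equal correlation | 1−2ρ²/(1+ρ) | 0.862 → 0.59 SD | 0.667 → 0.52 SD | 0.424 → 0.42 SD |

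**ANCOVA on Day 0 against raw change.** The variance reduction is 1 − (1−ρ²)/(2(1−ρ)) = (1−ρ)/2, that is 35%, 25% and 15%.

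**Adding Day -28.** Under equal correlation, variance falls by a further 1 − 0.862/0.91 = 5%, 1 − 0.667/0.75 = 11% and 1 − 0.424/0.51 = 17%. Days -28, 0 and 28 are equally spaced, so under a first-order autoregressive pattern the correlation of Day -28 with Day 28 is ρ². The partial covariance given Day 0 is then ρ² − ρ × ρ = 0, and Day -28 adds nothing.

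**Can a reader rebuild the interval from the planned tables?** If n, mean and SD of change are tabulated by arm, yes. If only visit-level AUC6.2 is tabulated, the SD of change also needs the within-subject correlation, which is not in the list. Over the assumed range that alone moves the half-width from 0.76 to 0.50 SD.

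**The case against.** **The SAP may supply the contrast.** The protocol leaves technical detail to an SAP that is not shown, and choice of model and covariates is ordinary SAP content. This stands for covariates and model details. It does not cover the contrast and its interval: Section 17 claims to hold the principal features, and how the primary difference is estimated is one of them. If the SAP adds it, Section 17.5.1 should still say so.

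**A descriptive study is legitimate.** Section 17.2 openly reports that no formal sample size calculation was made. No hypothesis test is needed, but an estimate with an interval is itself descriptive and serves the stated comparison.

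**Change from baseline is not an error.** This stands. ANCOVA is a gain in precision, not the correction of a bias.

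**Stronger readings that the documents do not support.**
- A reader might infer that neither pre-randomization measurement is used, or that chance baseline imbalance is left uncorrected. Day 0 is the defined baseline and enters through the change, which subtracts it in full. Only Day -28 has no stated role beyond summaries by visit.
- A reader might infer that the trial cannot answer its question. The necessary data are collected and individual values are listed; what is missing is the commitment to estimate and report the contrast.
- A reader might expect a large, assured gain from using both baselines. That needs equal correlation between visits. Also, by Section 8.1 the standard toothpaste is handed out and the teeth are professionally cleaned at Visit 2 after the measurements, so Day -28 is not a replicate of Day 0.
- Because the trial is open-label and the SAP is one "which will be signed and approved prior to database lock", a reader might infer that the analysis will be chosen after arm-level results are seen. The protocol does not say that the SAP authors see those results, and approval before lock is common practice. That is a separate matter.

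**Conclusion.** The concern holds in this form: the analysis text of the primary endpoint does not deliver the quantity that the endpoint defines. Section 17.5.1 commits to no between-arm estimate, no interval and no baseline adjustment. This rests on the text alone and needs no assumption.

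The size does rest on assumptions: 20 evaluable per arm, equal SDs, and ρ between 0.3 and 0.7. The unreported uncertainty is then a half-width of 0.76 to 0.50 SD for raw change. Adjusting for Day 0 brings it to 0.61 to 0.46 SD. The additional benefit of Day -28 lies between nothing and 17% of the remaining variance, depending on a correlation pattern that the documents do not give, so it should not carry the argument.

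**What to change.** In Section 17.5.1, and in the SAP to match, state that:

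- the primary analysis estimates the ZYN Dry minus ZYN Moist difference in Day 28 AUC6.2 with a two-sided 95% CI, from an ANCOVA with treatment and Day 0 AUC6.2. With Day 0 in the model, analysing Day 28 or the change gives the same treatment estimate, so the endpoint is preserved;
- AUC6.2 is one value per subject, with the four measured sites (Section 11.3.1) combined by a rule fixed in advance;
- the analysis includes randomized subjects with both Day 0 and Day 28 values. The full analysis set is all randomized subjects and nothing is imputed (Sections 17.1 and 17.3.1), so this is a complete-case analysis and should be described as one;
- the Section 17.1 summaries by arm and visit are supportive.

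Day -28 AUC6.2 may be added as a second covariate if this is prespecified, on the understanding that its gain is uncertain. Section 9.9 describes no stratification, so no stratification term is needed.

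The cost is protocol and SAP wording and a few lines of code. No new data, visits or subjects are required.

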## 17.6 Analysis of secondary endpoints

### 17.6.1 *Dental plaque acidogenicity*

The difference in dental plaque acidogenicity will be calculated from the start of tobacco-based snus substitution with either ZYN Dry or ZYN Moist (Visit 3) until the end of the study (Visit 5). The assessment of dental plaque acidogenicity will be described using AUC6.2 to the observed dental plaque acidogenicity and presented using summary statistics

### 17.6.2 *Number of cariogenic microorganisms in dental plaque*

The difference in the number of cariogenic microorganisms in dental plaque will be evaluated, graded, and calculated from the start of tobacco-based snus substitution with either ZYN Dry or ZYN Moist (Visit 3) until the end of the study (Visit 5) and presented through descriptive statistics.

